8.1 Primary objective

8.1.1 Patient characteristics and drug utilization

- To provide a description of patients who are prescribed oral rivaroxaban for the first time in comparison with those who are prescribed standard of care for the first time, and describe the characteristics of rivaroxaban use (including indication, dose and duration).
- To determine time-trends in the characteristics of first-time use of rivaroxaban.

8.1.2 Safety and effectiveness outcomes

- To study the occurrence of hospitalization or referral to a specialist from primary care for three bleeding events (primary safety outcomes): (a) intracranial haemorrhage, (b) gastrointestinal bleeding and (c) urogenital bleeding among users of rivaroxaban (for DVT/PE treatment, SPAF and ACS) in comparison with individuals receiving current standard of care.

8.2 Secondary objectives

- To study the occurrence of hospitalization for bleeding events not specified as primary safety outcomes (“other bleeding”), in comparison with individuals receiving current standard of care (secondary safety outcome).
- To study the occurrence of non-infective liver disease (secondary safety outcome).
- To study outcomes related to effectiveness (DVT/PE, ischaemic stroke, myocardial infarction).
- To study all-cause mortality.
- To conduct sub-group analysis of safety and effectiveness outcomes in populations of special interest:
 - patients with decreased renal function
 - elderly patients
 - patients with cardiovascular comorbidities e.g. hypertension or diabetes.

9 Research methods

9.1 Study design

This study has a cohort design including nested case–control analyses.

Cohorts of first-time users of either rivaroxaban or comparators will be identified using the date of first prescription (index date) of the respective drug (index drug) (Figure 1).

A patient will be considered eligible to enter the study cohort as a first-time user of rivaroxaban or a first-time user of “standard of care” when he or she has a first prescription of the drug recorded during the enrolment period. In the UK, for VTE prevention, DVT/PE treatment and SPAF, standard of care is treatment with the most widely used vitamin K antagonist, warfarin, and for the secondary prevention of ACS, standard of care is antiplatelet drug(s) such as low-dose acetylsalicylic acid, clopidogrel, dipyridamole, prasugrel, ticlopidine and ticagrelor.

Patients who have any record of being prescribed their index drug prior to the enrolment period or who qualify as members of both cohorts on the same day, will be excluded. If a patient qualifies as first-time user of both rivaroxaban and “standard of care” comparison drug during the enrolment period, she/he will be assigned to the cohort of drug first prescribed during the enrolment period, with the date of this prescription being the index date.

Many patients with ACS have a history of ischaemic heart disease for which platelet inhibition is standard treatment, and thus exclusion of patients with prior use of platelet inhibitors risks excluding a majority of typical ACS patients. Therefore, those who have been using one or more platelet inhibitors will remain eligible to enter the study.

Standard of care for ACS patients is combination therapy, and as such cohort assignment will be based on first use of rivaroxaban (in combination with aspirin or clopidogrel, or multi-antiplatelet therapy), or use of aspirin and clopidogrel and/or other antiplatelet medications.

Study subjects for DVT/PE treatment and SPAF, where the comparator is warfarin, will be categorized as naïve or non-naïve patients according to their previous use of any anticoagulant/comparator drugs (Figure 1). Naïve patients will be those without a previous prescription recorded before the index date. Non-naïve patients will be those with one or more relevant prescriptions recorded before the index date. Ascertainment of naïve/non-naïve status will also be confirmed by Read Code in addition to Drug Codes, e.g. Read Codes for warfarin monitoring, INR values >2, as this may be recorded in the absence of a Drug Code for warfarin.

Non-naïve patients will be further subdivided into recent switchers (patients exposed to the other anticoagulant/comparator in the 6 months prior to the index date) and distant switchers (patients exposed to the other anticoagulant/comparator more than 6 months prior to the index date).

[figure not shown]

Figure 1 Subdivision of study cohorts for DVT/PE treatment and SPAF.

Data collected for comparison of cohorts is described in [Section 9.3](#). The characteristics of the two study cohorts in the first year and subsequent years of the enrolment period will be compared.

Strengths of the study pertaining to the research question include:

- It uses observational data from routine clinical practice with no selection and no possibility to influence prescribing behaviour.
- Manual review of free text comments, questionnaires sent to primary care practitioners (PCPs) and cross-validation with hospital episode statistics (HES) in a subgroup of practices are possible, allowing for robust validation of outcomes.
- THIN is a well-validated resource for pharmacoepidemiology research (see [Section 9.2](#)).

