- The prevention of stroke and systemic embolism in adult patients with non-valvular atrial fibrillation (stroke prevention in atrial fibrillation [SPAF]) with one or more risk factors, such as congestive heart failure, hypertension, age \geq 75 years, diabetes mellitus, prior stroke or transient ischaemic attack (20 mg rivaroxaban od).
- The prevention of venous thromboembolism (VTE) in adult patients undergoing elective hip or knee replacement surgery (recommended dose: 10 mg rivaroxaban od for 35 days following hip replacement surgery and 14 days following knee replacement surgery).
- Co-administered with acetylsalicylic acid (ASA) alone or with ASA plus clopidogrel or ticlopidine, for the prevention of atherothrombotic events in adult patients after an acute coronary syndrome (ACS) with elevated cardiac biomarkers (recommended dose 2.5 mg bid).

As is the case with other anticoagulants, clinical studies of rivaroxaban have identified haemorrhage as an important safety outcome ([Lassen, Ageno et al. 2008](#); [Turpie, Lassen et al. 2009](#)). A post-authorization safety study programme is planned for several European countries. This document summarizes the design of a population-based study to characterize new users of rivaroxaban, assess patterns of drug utilization, including adherence to label recommendations, and to assess the risk of bleeding associated with rivaroxaban treatment compared with the standard of care in routine clinical practice in the UK, for ACS, DVT/PE treatment and SPAF. For DVT/PE treatment and SPAF, standard of care is treatment with the most widely used vitamin K antagonist, warfarin, and for the secondary prevention of ACS, standard of care is antiplatelet drug(s) such as low-dose acetylsalicylic acid, clopidogrel, dipyridamole, prasugrel, ticlopidine and ticagrelor.

8 Research questions and objectives

This post-authorization study was designed to assess patterns of drug utilization and to quantify outcomes related to safety and effectiveness in new users of rivaroxaban compared with new users of standard of care.

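### Section 9.1 does not reconcile the general cohort-entry rules with the ACS assignment paragraph, and leaves the index date of continuing antiplatelet users undefined

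*Protocol*

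**What the plan says.** Protocol section 9.1 begins with rules for all indications. A patient enters a cohort "when he or she has a first prescription of the drug recorded during the enrolment period", and the index date is the date of that prescription. Two exclusions follow. The first covers "Patients who have any record of being prescribed their index drug prior to the enrolment period". The second covers patients "who qualify as members of both cohorts on the same day, will be excluded". Anyone who qualifies for both cohorts on different days is handled by order: "she/he will be assigned to the cohort of drug first prescribed during the enrolment period", with that prescription as the index date.

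The same section names the comparator by indication. It is warfarin for the venous and atrial fibrillation indications, but "for the secondary prevention of ACS, standard of care is antiplatelet drug(s) such as low-dose acetylsalicylic acid, clopidogrel" and other named agents. Section 7 describes rivaroxaban in ACS as "Co-administered with acetylsalicylic acid (ASA) alone or with ASA plus clopidogrel or ticlopidine". The background treatment of the rivaroxaban arm is therefore drawn from the comparator drugs.

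Two ACS paragraphs close the entry rules. One explains that many ACS patients already take platelet inhibitors and concludes that "those who have been using one or more platelet inhibitors will remain eligible to enter the study". The other states that "cohort assignment will be based on first use of rivaroxaban (in combination with aspirin or clopidogrel, or multi-antiplatelet therapy"), or else on use of aspirin and clopidogrel and/or other antiplatelets. Section 8 describes the study as new users against new users. The naïve/non-naïve split in section 9.1 applies to DVT/PE treatment and SPAF only.

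**The concern.** The same-day exclusion and the first-drug rule suit a comparison in which a patient takes one drug or the other, as with warfarin. They do not suit ACS, where rivaroxaban is added to the comparator drugs. For some ACS patients the general rules and the ACS paragraph give different answers, and no precedence is stated.

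Three things are at stake.

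- **Cohort membership.** Two programmers following the same text could build different ACS arms.
- **Time zero.** Rivaroxaban patients enter at first use. The comparator limb speaks only of *use*, so a continuing antiplatelet user might enter at what is in effect a repeat prescription.
- **Attribution of bleeds.** If a patient sits in the comparator cohort and rivaroxaban is added later, bleeding on rivaroxaban could be counted against standard of care.

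ACS is one of the three indications in the primary safety objective (section 8.1.2), so this bears on a primary comparison.

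**Working it through.** No figure in the protocol bears on this point; the study size in section 9.5 concerns warfarin only. The check is to apply each set of rules to the same patients.

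**Set-up.** Take an ACS patient whose first rivaroxaban prescription falls within enrolment. Treat antiplatelets as one class (an assumption; section 9.1 does not say whether first use is judged by class or by drug). Vary only the date of the first antiplatelet prescription.

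| First antiplatelet prescription | General rules | ACS paragraph |
|---|---|---|
| (a) before the enrolment period | rivaroxaban | rivaroxaban |
| (b) within enrolment, before rivaroxaban | comparator | rivaroxaban |
| (c) same day as rivaroxaban | excluded | rivaroxaban |
| (d) after rivaroxaban | rivaroxaban | no conflict |

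**Reasoning by row.**

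- (a) The prior-use exclusion concerns the patient's own index drug. For a rivaroxaban starter that is rivaroxaban, so earlier antiplatelets do not exclude. Some doubt remains: the ACS exception also makes this patient eligible as a comparator, and an antiplatelet prescription in enrolment may precede rivaroxaban.
- (b) The patient qualifies for both cohorts on different days, so the first-drug rule selects the antiplatelet. The ACS paragraph looks to first use of rivaroxaban in combination.
- (c) The patient qualifies for both on one day and is excluded. The ACS paragraph describes exactly this combination as rivaroxaban use. Section 9.9 says that prescriptions started in hospital may be missed, so both drugs first appearing together in primary care is plausible, though the protocol does not say how often.
- (d) Rivaroxaban comes first under the general rules, and the ACS paragraph does not oppose that.

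The rules conflict in (b) and (c) only, two of the four orders. If first use is judged drug by drug, a long-term aspirin user who starts clopidogrel in enrolment and then rivaroxaban moves from (a) to (b).

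**Index date.** The general definition is the date the drug was first prescribed. For a continuing antiplatelet user that date may lie before enrolment. Section 9.1 gives no substitute date and does not tie entry to the date of an ACS event. The rivaroxaban limb has a definite start; the comparator limb does not.

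**Follow-up.** Section 9.7.2 defines current use by supply of the index drug plus 7 days and states no rule for adding the other cohort's drug. Because rivaroxaban is added to antiplatelets in ACS, antiplatelet supply may continue. A row (b) patient routed to the comparator would then remain a current comparator user while taking rivaroxaban.

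**The case against.** The strongest reply is that a specific rule placed after general ones governs its own case. The ACS paragraph gives its reason, that ACS treatment is combination therapy, and sends combination users to rivaroxaban. This is a reasonable reading and may be what was intended. It does not settle the matter. The ACS exception expressly relaxes only prior use and is silent on the same-day and first-drug rules. A patient on aspirin and clopidogrel who later adds rivaroxaban also meets both limbs of the ACS sentence, and nothing says which limb applies or from when.

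A second reply is that keeping prior platelet-inhibitor users is a disclosed choice with a stated reason. That stands: it is a trade-off, not a self-contradiction. The gap is the missing index date for the patients so admitted.

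A third is that section 9.3.1 collects antiplatelet use in the year before the index date and section 9.7.2.1 adjusts for baseline medication where numbers allow. That helps with confounding by prior use but cannot repair assignment or time zero. Detailed handling of person-time may be left to an analysis plan that is not shown; cohort membership and index date are fixed, inconsistently, in this document.

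A reader might infer that the ACS comparison loses its rivaroxaban arm. The documents do not support this, since rows (a) and (d) reach the rivaroxaban cohort even under the general rules alone. A reader might also infer that most comparators would be prevalent users past their early bleeding risk. The protocol says only that excluding prior users risks losing most typical ACS patients. A prior aspirin user who starts a second antiplatelet has a new regimen, and prior users are eligible in both arms.

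**Conclusion.** The point holds as an unreconciled conflict between two sets of entry rules in section 9.1, together with an undefined index date for continuing antiplatelet users in the ACS comparator. The conflict affects ACS patients who start an antiplatelet within enrolment, on the same day as rivaroxaban or before it. Their number cannot be derived, because the protocol gives no counts by order of prescription. The table assumes that antiplatelets are judged as a class and that the general rules are read literally.

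It does not follow that the ACS rate ratio would be uninterpretable. If the ACS paragraph is meant to govern, assignment is largely settled, leaving time zero and the handling of added rivaroxaban to be specified. The DVT/PE and SPAF comparisons with warfarin, and the warfarin-based study size, are unaffected. The point still warrants correction before the ACS cohorts are built, because the choice of rule changes who is in each arm and when follow-up starts.

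**What to change.** Amend section 9.1, with a matching sentence in section 9.7.2:

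1. State that for ACS the assignment paragraph governs, and that the same-day exclusion, the first-drug rule and the prior-use exclusion do not apply to background antiplatelets.
2. Define one index date for both ACS arms, for example the first prescription of the regimen after an ACS event recorded in the enrolment period.
3. State that comparator person-time ends when rivaroxaban is added and that later time counts as rivaroxaban time.
4. Adjust for, or stratify by, prior antiplatelet use in ACS, as a counterpart to the naïve/non-naïve split made for DVT/PE treatment and SPAF.

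The prescriptions and diagnoses needed are already among the planned data (sections 9.3.1 and 9.4). The cost is protocol wording, some extra cohort programming and a smaller ACS comparator, because antiplatelet users without an ACS event in the enrolment period would no longer enter it. Anchoring on the event is one workable choice; the minimum is a statement of precedence and a defined comparator index date.

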9.3 Variables

9.3.1 Patient characteristics and drug utilization

The following variables, including risk factors/potential confounders for the outcomes under study, will be collected for comparison between the two cohorts:

- age and sex distribution at index date; 
- dose of index drug at index date and duration of treatment (including pack size); 
- diagnosis associated with the prescribing of the index drug; 
- proportion of patients defined as naïve, non-naïve, recent switchers and distant switchers; 

- type and duration of other anticoagulant use before the index date among the non-naïve group; ✓
- number of pregnant women at index date; ✓
- number of pregnancies after the index date; ✓
- use of specific prescribed medications both in the year before the index date and following the index date, confirming the ACS indication: antiplatelet drugs (low-dose acetylsalicylic acid, clopidogrel, dipyridamole, prasugrel, ticlopidine and ticagrelor); ✓
- use of other prescribed medications both in the year before the index date and following the index date: anticoagulants (including dabigatran etexilate and apixaban), antiarrhythmic drugs, antihypertensive drugs, statins, anti-diabetic agents, non-steroidal anti-inflammatory drugs, oral steroids, acid-suppressive drugs, disease-modifying anti-rheumatic drugs, antidepressants, antipsychotic drugs, oral contraceptives, hormone-replacement therapy, strong inhibitors of either cytochrome P450 3A4 or P-glycoprotein (e.g. the systemic azole antimycotics ketoconazole, itraconazole, voriconazole and posaconazole and the HIV-protease inhibitor ritonavir), strong CYP3A4 inducers (e.g. rifampicin, phenytoin, carbamazepine or phenobarbital) and fluconazole; ✓
- renal disease based on diagnoses, most recently recorded before the index date and in following the index date, with estimated glomerular filtration rate (eGFR) or creatinine clearance (CrCl) to be obtained where available; ✓

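### The single-cohort rule leaves in-period comparator starters who later begin rivaroxaban out of the rivaroxaban description, which biases the warfarin-switcher share downward by an amount that grows with calendar time

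*Protocol*

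**What the plan says.** Section 9.1 builds two cohorts of new users. A patient who qualifies for both on different days of the enrolment period is handled by one sentence: "she/he will be assigned to the cohort of drug first prescribed during the enrolment period", "with the date of this prescription being the index date". There is no second index date for a later start of the other drug.

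The prior-use exclusion in the same section covers only a patient's own index drug: "Patients who have any record of being prescribed their index drug prior to the enrolment period" are excluded. Someone who took warfarin before enrolment opened can therefore still enter the rivaroxaban cohort.

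The descriptive objectives in section 8.1.1 are wider than this rule: "To provide a description of patients who are prescribed oral rivaroxaban for the first time" and "To determine time-trends in the characteristics of first-time use of rivaroxaban". Section 9.3.1 lists among the variables the "proportion of patients defined as naïve, non-naïve, recent switchers and distant switchers", and section 9.1 adds that "The characteristics of the two study cohorts in the first year and subsequent years of the enrolment period will be compared". Section 9.7.1 gives the descriptions overall and by indication, naïve status and switching status.

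No section defines a separate rivaroxaban population for the descriptive part. Section 9.2 draws the outcome study from the source population of the utilisation study, and the limitations in section 9.9 do not mention the effect.

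**The concern.** The rule treats two kinds of warfarin-to-rivaroxaban switcher differently, according to when warfarin began. If it began before enrolment, the patient enters the rivaroxaban cohort as a switcher. If the patient first qualified as a warfarin user during enrolment, the patient never enters it. Early in enrolment almost all switchers are of the first kind. After several years many are of the second kind, so a growing part of the switchers goes unrecorded.

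At stake is a primary objective. The naïve and switcher proportions, and their change from the first year to later years, would mix real prescribing patterns with an effect of cohort assignment. The interim drug-utilisation reports at 2 and 4 years would be built on progressively more depleted rivaroxaban cohorts. Section 9.7.2.7 also relies on the descriptive part to reveal unexpected biases for the outcome analyses, so a distorted description could mislead decisions taken there.

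**Working it through.** The protocol states no figure on this point. Its one calculated figure, the study size in section 9.5, does not enter the argument.

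**What the rule does, case by case**

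- Warfarin in 2010, rivaroxaban in 2013: prior warfarin use bars the warfarin cohort; enters the rivaroxaban cohort as a switcher.
- First warfarin in 2013, rivaroxaban in 2015: qualifies for both; warfarin cohort only, indexed in 2013.
- No earlier anticoagulant, rivaroxaban in 2015: enters the rivaroxaban cohort as naïve.

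The second patient is a first-time rivaroxaban user under 8.1.1 but is not counted as one. The direction of the bias follows from this alone.

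**Inputs for an illustration of size**

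- From the protocol: enrolment opens the day after the DVT authorisation (Abstract, Milestones: 9 December 2011; section 9.2) and closes on 31 December 2017. That is 10 December 2011 to 31 December 2017, or 6.06 years.
- Assumed: the true share p of rivaroxaban starters who switch from warfarin is constant over time. The main case is 30%.
- Assumed: the warfarin population is in steady state, and time on warfarin before the switch is exponential with mean D = 1, 2 or 4 years.

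**Formulae**

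- A switcher at enrolment time t is retained only if warfarin began before enrolment, with probability exp(−t/D).
- Mean retention over the interval a to b: v = D × [exp(−a/D) − exp(−b/D)] / (b − a).
- Recorded share = p·v / (1 − p + p·v).
- If a fraction q of non-naïve users is untouched by the rule, replace v by q + (1 − q)·v.

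**Worked example, p = 0.30, D = 2**

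- Year 1 (0 to 1): v = 2 × (1 − exp(−0.5)) = 0.787. Share = 0.2361 / (0.70 + 0.2361) = 25.2%.
- Year 6 (5 to 6.06): v = 2 × (exp(−2.5) − exp(−3.03)) / 1.06 = 0.0637. Share = 0.0191 / (0.70 + 0.0191) = 2.7%.

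**Recorded share (%) when the true share is 30% in every year**

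| Assumption | Yr 1 | Yr 2 | Yr 3 | Yr 4 | Yr 5 | Yr 6 |
|---|---|---|---|---|---|---|
| D = 1 | 21.3 | 9.1 | 3.5 | 1.3 | 0.5 | 0.2 |
| D = 2 | 25.2 | 17.0 | 11.0 | 7.0 | 4.4 | 2.7 |
| D = 4 | 27.5 | 22.8 | 18.7 | 15.2 | 12.2 | 9.7 |
| D = 2, 10% untouched | 25.7 | 18.5 | 13.4 | 10.0 | 7.7 | 6.3 |
| D = 2, 25% untouched | 26.5 | 20.7 | 16.7 | 14.1 | 12.4 | 11.3 |
| D = 2, 50% untouched | 27.7 | 24.0 | 21.6 | 20.1 | 19.2 | 18.6 |

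Over the whole enrolment period with nobody untouched, the rule drops 84%, 69% and 49% of these switchers for D = 1, 2 and 4. At p = 30% that is 25%, 21% and 15% of all first-time rivaroxaban users.

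Other true shares give the same pattern. For D from 1 to 4 years, a true 20% is recorded as 13.6–18.1% in year 1 and 0.1–5.9% in year 6. A true 50% is recorded as 38.7–46.9% and 0.4–20.1%.

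The calculation covers warfarin, where section 9.1 defines naïve and switcher status (DVT/PE treatment and SPAF). It does not extend to ACS, where section 9.1 keeps earlier platelet-inhibitor users eligible.

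**The case against.** Mutually exclusive cohorts are a recognised choice. Objective 8.1.1 describes rivaroxaban users against standard-of-care users, and section 9.7.1 computes odds ratios between the cohorts; overlap would put one person on both sides. This stands as a reason for exclusive cohorts in between-cohort comparisons. It does not justify leaving these patients out of the rivaroxaban description and its time trends.

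The plan also contains partial mitigation. Section 9.7.1 stratifies by naïve status, and naïve rivaroxaban starters are untouched by the rule, so trends within that stratum remain interpretable. Section 9.3.1 collects anticoagulant use after the index date, so later rivaroxaban use is visible inside the warfarin cohort. Neither puts the missing patients back into the rivaroxaban description at their rivaroxaban date.

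Stronger readings are tempting, but the protocol does not support them:

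- A reader might infer that everyone who took warfarin during enrolment is removed, or that only pre-2011 warfarin users remain as switchers. The rule reaches only patients who qualify as new users of both drugs. Pre-enrolment warfarin users who restart still enter. So do patients whose warfarin is seen only through Read codes or INR, and users of other anticoagulants such as dabigatran or apixaban, whom section 9.1 counts as non-naïve.
- A reader might infer that the remaining switchers are ever longer-term warfarin users. A patient with a short course before enrolment and rivaroxaban in 2016 is a distant switcher, not a long-term user.
- A reader might infer definite shifts in age, comorbidity or prior bleeding. The document gives no basis for their direction or size.

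**Conclusion.** The point holds as a bias of known direction and unknown size. Patients who qualify as first-time comparator users during enrolment and later start rivaroxaban are missing from the population that objective 8.1.1 describes. The recorded share of switchers from warfarin is therefore too low, increasingly so in later years, and the first-year against later-year comparison is distorted accordingly.

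The size rests on assumptions, since the protocol gives neither the switching share nor the time on warfarin. With a true 30% share and a mean of 1 to 4 years, the recorded share falls from 21–28% to 0.2–10%. With a 2-year mean and half of non-naïve users unaffected, the fall is from about 28% to 19%. It would be too strong to say that the reports will show a fall: a real rise in switching could offset it.

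The change should be made because a primary descriptive objective is affected and the remedy is cheap. The point is no criticism of exclusive cohorts in the comparative outcome analysis.

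**What to change.** In section 9.1, limit the single-cohort rule to the comparative outcome analysis. For the rivaroxaban description and time trends (8.1.1, 9.3.1, 9.7.1), define the population as every otherwise eligible patient with a first-ever rivaroxaban prescription in the enrolment period. Index each at that date and classify as naïve, recent switcher or distant switcher at that date, regardless of an earlier in-period comparator start. Such a patient may also be described in the comparator cohort at the earlier date.

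For the between-cohort odds ratios in 9.7.1, either keep the exclusive cohorts or allow the overlap, state its extent and use a robust variance.

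Reporting by calendar year how many rivaroxaban starters the single-cohort rule would have left out would replace the assumptions above with the actual size.

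The cost is one rule change and a re-run of the descriptive tables on data already extracted. The downside is that some patients appear in both descriptive cohorts, which the report must say.

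### The ACS comparator is defined in two ways and the antiplatelet background of the two cohorts is not aligned, so the ACS bleeding ratio can be biased in either direction

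*Protocol*

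**What the plan says.** ACS is one of the three indications named for the primary bleeding objective (section 8.1.2). The protocol describes its comparator three times:

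- Section 7 and the eligibility paragraph of section 9.1 use the same words: "for the secondary prevention of ACS, standard of care is antiplatelet drug(s) such as low-dose acetylsalicylic acid, clopidogrel, dipyridamole, prasugrel, ticlopidine and ticagrelor".
- The ACS assignment paragraph, later in section 9.1, says: "Standard of care for ACS patients is combination therapy, and as such cohort assignment will be based on first use of rivaroxaban". On the comparator side, entry rests on "or use of aspirin and clopidogrel and/or other antiplatelet medications".

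For the rivaroxaban ACS cohort, that last paragraph allows use "in combination with aspirin or clopidogrel, or multi-antiplatelet therapy". Section 7 describes the indication as "Co-administered with acetylsalicylic acid (ASA) alone or with ASA plus clopidogrel or ticlopidine". Both allow a single background agent.

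On prior use, section 9.1 generally excludes anyone with an earlier record of the index drug, but for ACS it says that "those who have been using one or more platelet inhibitors will remain eligible to enter the study".

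On analysis, section 9.7.2.1 commits to rate ratios adjusted for age and sex. Adjustment for baseline medication, comorbidity and indication depends on sufficient numbers and data, and the nested case-control analysis depends on enough final cases. Section 9.3.1 collects use of the named antiplatelets in the year before the index date and after it.

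**The concern.** Two programmers following this text could build different ACS reference cohorts. One would admit a patient on low-dose aspirin alone and the other would not. The choice also affects the index date: under the drug(s) wording it can be the first prescription of a single agent, while under the combination wording it would be when combination use begins. Because prior platelet-inhibitor users stay eligible, it is also unclear which prescription makes an ACS comparator patient a first-time user.

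If bleeding risk rises with the number of antiplatelets, the ACS ratio mixes two things: the effect of adding rivaroxaban, and any difference between the cohorts in the number of background agents. Age and sex adjustment does not separate them. In a safety study both directions matter, since an upward bias can create a bleeding signal and a downward bias can hide one.

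**Working it through.** **What the plan's own figure covers.** The only sizing figure (section 9.5) concerns haemorrhagic stroke against warfarin. At 5 per 1000 person-years, 12,000 and 48,000 person-years give 60 and 240 expected events. The standard error of the log rate ratio is √(1/60 + 1/240) = 0.144. With a true ratio of 1, a margin of 1.5 and two-sided 0.05 (assumed, because alpha is not stated), power is Φ(0.405/0.144 − 1.96) = 80.2%. The stated figure reproduces. It does not depend on the ACS comparator, and the protocol gives no corresponding figure for ACS.

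**Which patients the wording admits.**

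- Drug(s), in section 7 and the eligibility paragraph of 9.1: one agent is enough.
- Combination therapy, in the ACS assignment paragraph of 9.1: more than one agent is implied.
- The and/or entry clause in that same paragraph: no minimum number, no concurrency window and no index-date rule.
- Rivaroxaban ACS cohort: one agent or several.

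**Effect on the ratio.** Let b be the bleeding rate on one antiplatelet without rivaroxaban, kb the rate on two or more, and θ the rivaroxaban ratio at equal background. Let fr and fc be the shares on a single antiplatelet in the rivaroxaban and comparator cohorts.

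- Rivaroxaban rate = θ·b·[fr + (1 − fr)k]
- Comparator rate = b·[fc + (1 − fc)k]
- Bias factor = [fr + (1 − fr)k] / [fc + (1 − fc)k]

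For k above 1, the factor exceeds 1 when fc > fr, equals 1 when the shares are equal, and is below 1 when fc < fr. The protocol supplies none of k, fr or fc, so all values below are assumptions.

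At k = 1.5:

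- fr = 0, fc = 0.5: 1.5 / 1.25 = 1.20
- fr = fc: 1.00
- fr = 0.5, fc = 0: 1.25 / 1.5 = 0.83

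The same scenarios across k, with one intermediate case:

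| fr | fc | k = 1.25 | k = 1.5 | k = 2 |
|---|---|---|---|---|
| 0 | 0.5 | 1.11 | 1.20 | 1.33 |
| 0.25 | 0.5 | 1.06 | 1.10 | 1.17 |
| equal | equal | 1.00 | 1.00 | 1.00 |
| 0.5 | 0 | 0.90 | 0.83 | 0.75 |

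Over k from 1.25 to 2 and all shares from 0 to 1, the factor runs from 0.50 to 2.00.

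**Requiring two or more agents in the comparator only.** This sets fc = 0, and the factor becomes 1 − fr(1 − 1/k), which is never above 1. At k = 1.5 it is 0.92, 0.83 and 0.75 for fr = 0.25, 0.5 and 0.75.

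**The case against.** The strongest reply is that the conflict is mainly one of wording. Section 7 is background, drug(s) covers the plural, and the ACS assignment paragraph, being the specific rule, would normally govern. This has some force, but the specific rule does not settle the matter, because its and/or clause leaves open whether one agent suffices.

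A second reply is that the plan already has the means to deal with imbalance. Antiplatelet use is collected, section 9.7.1 compares co-medications by indication, section 9.7.2.1 foresees adjustment for baseline medication, and section 9.7.2.7 allows biases seen in the utilization data to be accounted for. How a covariate is coded can also be left to an analysis plan. All this is fair and could reduce the imbalance. But the medication adjustment is conditional, and an analysis plan cannot follow two entry rules for the same cohort.

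Two stronger readings are tempting and are not supported:

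- A reader might infer that single-agent comparators will inflate the rivaroxaban ratio. That needs the comparator to have the larger single-agent share. The documents allow single-agent background in the rivaroxaban cohort too and give neither share, so the direction is unknown.
- A reader might infer that the assignment paragraph already requires two or more concurrent agents at index, so that enforcing this in the comparator is the remedy. The paragraph states no such minimum or window, and the restriction applied to the comparator alone could push the ratio down.

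**Conclusion.** The point holds as an inconsistency in cohort definition together with a possible bias of unknown direction. One indication in the primary safety objective has no single comparator cohort, and the only unconditional comparative analysis adjusts for age and sex alone.

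The size cannot be taken from the documents. With k = 1.5 the illustrative factors are 1.20, 1.00 and 0.83, depending only on the two single-agent shares. They rest on an assumed k, on assumed shares, and on a rivaroxaban effect that is the same on single and dual background. They also assume that the ratio is formed within ACS. Section 9.7.2.1 does not say so expressly, but section 9.7.2 estimates incidence by indication and the comparator differs between indications.

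The DVT/PE and SPAF comparisons against warfarin, and the study-size figure, are not affected.

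**What to change.** Reconcile section 7 and the two paragraphs of section 9.1 into one operational ACS cohort definition. It should state the minimum number of antiplatelet agents, the window that counts as concurrent use, the index date, and what counts as first use when earlier antiplatelet users remain eligible.

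Classify both cohorts by number of antiplatelets at index (one; two or more), using the prescription data already collected under section 9.3.1. Make the main ACS rate ratio stratified by or adjusted for that count as a fixed element of section 9.7.2.1, outside the conditional adjustments. Do not restrict only the comparator to two or more agents without this stratification.

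The cost is revised wording, one derived variable and somewhat less precision within ACS strata. This concerns only how the cohorts are defined and compared, not which therapy is right.
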